5.1.1 Identification of Primary and Historical patient cohorts

Care quality, utilization, and patient-reported outcomes will be collected on both the Historical and Primary cohort patients identified by participating clinics in their submissions directly to MNCM. Clinics will identify their Historical and Primary cohorts of care coordination patients and submit their name, date of birth, demographics, date of starting coordination, contact information, and insurance information through a secure data submission portal directly to MNCM. See **Appendix A: Patient data specifications** for complete specifications of data to be submitted by clinics to MNCM.

Clinic data submission will occur in two rounds, one for the Historical Cohort (care coordination enrollment dates from January 2018–February 2019) and one for the Primary Cohort (care coordination enrollment dates January 2021–December 2021). MNCM will assign a unique study ID to each patient in these datasets, which will be used as a linkage to the quality, utilization, and patient-reported datasets described below while providing confidentiality.

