5.4 Patient Surveys (Historical and Primary Cohorts)

Patient surveys will be conducted to provide both contextual patient information and outcome data central to the study goals. The patient survey of the Historical Cohort will be conducted to provide information related to patient experiences during the COVID-19 pandemic. Surveys will solicit patient characteristics not otherwise available through the electronic health record (EHR), patient experiences with care coordination, and patient-reported outcomes, in the case of the Primary Cohort.

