5.4.1 Patient survey instrument design

Patient interviews will be used to inform closed-ended surveys. Both the Historical and Primary cohort surveys will include questions that provide validation of the coordination process at each clinic. The Primary Cohort will also provide the key patient-reported outcome measures as well as patient characteristics. The surveys will be designed using existing survey questions with known psychometric properties where they exist. When no existing questions match desired survey concepts, questions will be developed using known best-practices for question writing.⁴¹ Patient partners will fully be engaged in the development of the concepts, questions, and overall survey process design.

The surveys will be designed using unified mode design to minimize measurement error due to mixed mode implementation. Prior to full implementation, the surveys will be piloted with a small population similar to our target population for face validity, asking participants for their feedback on survey acceptability, length, and understanding (see Section 5.4.3). Ambiguous or difficult items will be adjusted and retested.

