outcomes, we will also evaluate a composite outcome representing the proportion of applicable care quality outcomes that are met by a given patient. We intend to primarily evaluate this proportion as a continuous variable in a linear or tobit regression model that follows the structure in equation (1) above with the inclusion of a patient's baseline composite outcome as a covariate. However, based on the empirical distribution, we may also evaluate transformations to binary or multilevel categorical versions of this outcome as warranted.

Utilization outcomes for Aim 1 analyses will be evaluated both as binomial (any occurrence vs. none) and as counts. GLMMs will follow the framework of equation (1) above, however, for the underlying distribution of count outcomes we will assume a Poisson (or negative binomial, as appropriate) distribution with a log (as opposed to logit) link function. We anticipate a similar modeling approach for quantitative analyses of the impact of care coordination type on patient-reported outcomes (again adapting assumptions of the underlying distribution and corresponding link function, specific to the nature of each outcome variable). The main exception will be that we will not have baseline values for patient-reported measures, given that they will only be collected at a single time point in follow-up. Reporting of medical costs as a secondary outcome will follow PCORI standards.⁵³

Primary results for Aim 1 analyses will be reported as odds ratios, rate ratios, or (beta) differences (comparing the medical/social care coordination model to the nursing/medical model), with 95% confidence intervals, for each study outcome.

All Aim 1 analyses as described above will be replicated for both the Primary and Historical cohorts, and reported separately. To evaluate whether cohort-specific estimates statistically differ with respect to a given outcome, we will estimate pooled (Primary + Historical) models and evaluate the significance of the Wald test for the interaction term (*Cohort*CC Type*). Additionally, for the Historical cohort, care quality and utilization outcomes may potentially be available for up to 3 years from the onset of care coordination. Where data is available, we will estimate the impact of care coordination type on 1-year, 2-year, and 3-year outcomes respectively, using the framework described above, within the Historical cohort.

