7.3.6.2 Population used to generate effect estimates

As described in Section 4.2.2, patients will be eligible for analyses if they have been designated for care coordination at a participating clinic and have not opted out of research. For utilization outcomes, inclusion will additionally require health insurance coverage from a participating payor. For patient-reported outcomes, inclusion will additionally require completion of the study survey. As described above, patients will be followed for health care quality and utilization outcomes over the 12 months preceding and the 12-36 months following the first observed enrollment in care coordination, and patient-reported outcomes will be collected by survey in the 6-18 months following first enrollment in care coordination (Primary Cohort only). For a discussion of analytic implications of selection by survey response, please see Section 7.3.6.1 above. Differences in survey respondents vs. non-respondents will be assessed for potential selection bias and potential impact on validity of results.

7.3.6.3 Timing of the outcome assessment relative to the initiation and duration of exposure

As described above, timing in the assessment of health care quality and utilization outcomes will account for outcomes in the 12 months preceding initiation of care coordination in comparison to outcomes in the 12 months following initiation of care coordination. Assessment of patient-reported outcomes will be collected in the 6-18 months following initiation of care coordination (Primary Cohort only). Patients' exposure time will be the observable duration of time spent in a care coordination program; they will be considered exposed for the entire follow-up period for each outcome. Exposure to the intervention (care coordination) will be determined at the patient level, whereas comparator status (choice of care coordination model) will be implemented by each clinic at the clinic level. Due to these conditions, sequential temporality will be ensured, and immortal time bias will not be applicable.

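### Section 7.3.1 carries the patient-reported outcomes into the Historical Cohort and a pooled cohort test, while 7.3.6.2 and 7.3.6.3 confine them to the Primary Cohort, and the plan does not say which governs

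*Combined protocol and SAP*

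**What the plan says.** Section 7.3.1 describes the quality and utilization models and then turns to patient-reported outcomes: "We anticipate a similar modeling approach for quantitative analyses of the impact of care coordination type on patient-reported outcomes". The one exception it makes for them is that they have no baseline value. The replication sentence follows: "All Aim 1 analyses as described above will be replicated for both the Primary and Historical cohorts, and reported separately". For the cohort comparison, "we will estimate pooled (Primary + Historical) models and evaluate the significance of the Wald test for the interaction term". Section 7.3.4 repeats that test and interprets it as timing relative to COVID.

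Section 5.1.1 agrees with the wide scope: "Care quality, utilization, and patient-reported outcomes will be collected on both the Historical and Primary cohort patients". Section 5.1.4 likewise speaks of a subset of both cohorts.

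Other sections are narrower:

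- 7.3.6.2: "patient-reported outcomes will be collected by survey in the 6-18 months following first enrollment in care coordination (Primary Cohort only").
- 7.3.6.3: "Assessment of patient-reported outcomes will be collected in the 6-18 months following initiation of care coordination (Primary Cohort only").
- 5.4 has the surveys supply "patient-reported outcomes, in the case of the Primary Cohort".
- 5.4.1: "The Primary Cohort will also provide the key patient-reported outcome measures as well as patient characteristics".
- 7.2.2 gives Historical power for care quality and utilization only.

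Table 3 lists general health status and rating of the primary care clinic as primary outcomes at 6 to 18 months. It marks body mass index as Primary Cohort only, but puts no such mark on the patient-reported outcomes.

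**The concern.** The analysis population for two primary outcomes is defined in two incompatible ways. An analyst who follows 7.3.1 has data to work with. The Historical survey (Appendix G) has a five-level general health item and the same 0-10 clinic rating as the Primary survey (Appendix H).

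That analyst would produce a Historical care-model effect and a cohort interaction for both outcomes, and 7.3.4 would have the interaction read as a COVID effect. If the difference between care models fades or grows with time since start, that change would appear as a difference between cohorts. The risk is greater because 6.8 accepts that strict masking is not possible. A scope left open could therefore be settled after results are known.

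**Working it through.** **Inputs**

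- Start dates (Appendix A): Historical 1 Jan 2018 to 28 Feb 2019; Primary 1 Jan 2021 to 31 Dec 2021.
- Survey completion (Section 10): Historical 15 Dec 2021; Primary 15 Nov 2022.
- Primary survey timeframe: Q3 2022 (Table 1); fall 2022 in the text of 2.2.2.
- Historical fielding start: not given. I assume 15 Aug 2021 (close of data submission in Appendix A) or 15 Sep 2021 (the submission milestone in Section 10).
- Pandemic onset: March 2020 (Appendix D). I count from 1 March.

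**Formula.** Shortest time since start = first survey date minus last start date. Longest = last survey date minus first start date. Months = days / 30.4375.

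**The plan's own figure.** If every Primary survey is answered on 1 Jul 2022, the shortest time is 182 / 30.4375 = 6.0 months and the longest is 546 / 30.4375 = 17.9. This reproduces the stated 6 to 18 months. Fielding through 15 Nov 2022 lengthens the upper end to 683 / 30.4375 = 22.4.

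**Time since start if 7.3.1 is followed**

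| Cohort and fielding window | Shortest | Longest |
|---|---|---|
| Historical, 15 Aug to 15 Dec 2021 | 899 days = 29.5 | 1,444 days = 47.4 |
| Historical, 15 Sep to 15 Dec 2021 | 930 days = 30.6 | 47.4 |
| Historical, all on 15 Dec 2021 | 1,021 days = 33.5 | 47.4 |
| Primary, as stated | 6 | 18 |
| Primary, 1 Jul to 15 Nov 2022 | 6.0 | 22.4 |

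The ranges do not overlap in any row. The gap depends on the assumed dates. It is 29.5 - 22.4 = 7.1 months with the earlier Historical start, and 30.6 - 22.4 = 8.2 with the later one. Against the stated 18-month limit it is 11.5 or 12.6 months.

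**Calendar time.** Historical fielding runs from 17.5 months (15 Aug start) or 18.5 months (15 Sep start) to 21.5 months after 1 March 2020. Primary fielding, 1 Jul to 15 Nov 2022, runs from 28.0 to 32.5 months after. No patient-reported value in either cohort predates the pandemic. The 12-month outcomes differ in this respect: the last Historical start, 28 Feb 2019, completes 12 months at the end of February 2020, so the before/after reading is sensible for them.

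**The duration covariate.** Section 7.3.6.4 enters follow-up duration, described as 6 to 18 months, as a covariate. A main effect of duration does not adjust a cohort-by-model interaction for a care-model effect that itself changes with time. A duration-by-model term would be needed. Because the ranges do not overlap, such a term could separate cohort from duration only by extrapolating across the gap.

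**The case against.** The strongest reply is that the specific provisions already point one way. Section 7.3.6.2 is the section on the population for effect estimates, and it says Primary Cohort only, as does 7.3.6.3. Table 3 and 7.3.6.4 use a 6 to 18 month window that the Historical survey cannot meet. Section 7.2.2 covers only quality and utilization, yet says it covers all primary outcomes for the Historical Cohort, which suggests that patient-reported outcomes were never meant to be among them. The longer Historical follow-up in 7.3.1 also names only quality and utilization. Sections 5.1.1 and 5.1.4 concern collection, and collecting an item does not commit the plan to estimating an effect from it.

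Most of this stands as evidence of intent, and it makes the narrow reading the more likely one. It does not remove the conflict. The replication sentence in 7.3.1 is unqualified, follows directly after the patient-reported models, and makes no exception for them beyond the missing baseline.

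A reader might infer more than the documents support:

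- **That the mismatched comparison will be run.** It arises only if 7.3.1 overrides 7.3.6.2 and 7.3.6.3.
- **That a detectable Historical or pooled difference can be set against the 1 point stated in 7.2.1.** That figure rests on the PROMIS-10 score with a standard deviation of 10. The Historical survey has no PROMIS scale, so the comparison has no basis.
- **That there is a fixed minimum gap in follow-up.** The fielding start is not given, and Section 10 calls its dates subject to change.

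**Conclusion.** The point holds as an unresolved inconsistency with a conditional consequence. Two of the primary outcomes have no single stated population. Under 7.3.1 they would be compared across cohorts at about 30 to 47 months versus 6 to 18 months (up to about 22), entirely within the pandemic period. The resulting interaction would be confounded with time since start and could not bear the interpretation given in 7.3.4. Under 7.3.6.2 and 7.3.6.3 no such estimate is produced.

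The Historical range rests on the assumed fielding start and the Section 10 milestones. The lack of overlap holds under every window tried. The Primary Cohort estimates of both outcomes are unaffected.

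**What to change.** In 7.3.1, qualify the replication and the pooled test, for example: *The Historical Cohort replication and the pooled cohort-by-model test cover care quality and utilization outcomes only.* Carry the same limit into 7.3.2, 7.3.3 and 7.3.4, which inherit the replication or the cohort contrast. Mark the patient-reported outcomes as Primary Cohort only in Table 3, and align 5.1.1 and 5.1.4. Section 7.2.2 would then be consistent as it stands.

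If Historical health status or clinic rating is shown, report it descriptively as a late outcome measured during the pandemic, with its own time window and no before/after-COVID reading.

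The cost is a few sentences in the SAP. The small downside is giving up a patient-reported cohort test that these data cannot support.

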7.3.2 Aim 2 Analysis

To identify the key components of care coordination that associate with study outcomes, we will use the general approach described for Aim 1 analyses, with minor adaptations. For the designated care coordination characteristics (Section 2.2), we will first tabulate descriptive summaries as described above. We will then evaluate a series of GLMMs to evaluate care coordination components (part of the vector of clinic-level independent variables W_{jk}) for each study outcome: 1) using the full model specification in Equation 1; and 2) stratified models restricted to the populations within care coordination type. These analyses will be replicated in each of the Primary and Historical cohorts as described in Aim 1 above. Taken together, we anticipate these sets of results will provide comprehensive evidence of the impact of individual components of care coordination on study outcomes. We may consider latent class analysis as a secondary means to classify differing approaches to care coordination for use in Aim 3 analysis.

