The primary strategy will involve requiring the lead care coordinator at each participating clinic to complete a survey that asks about each core component. This survey will be conducted in the fall of 2021, at a time when the clinics will have renormalized as COVID-19 pressures have declined. This timing will align with the Primary Cohort identification period (1/21-12/21), so it will provide a very specific verification of implementation models during the time the Primary cohort was being enrolled and receiving services. The response rate for this survey will be 100% because completing the survey is a requirement of participation in the study, which we have communicated to clinics throughout our recruitment process. We shall also ask the lead care coordinators whether any of these core components have changed in any significant way during the preceding 3 years (with a focus on 2018 to correspond with the Historical cohort) and whether they are expected to change in the next year. These surveys will be preceded by semi-structured interviews with about 20 care coordinators for the purpose of identifying every potentially important component of care coordination needed to be included in the survey. The study team will design the care coordination survey to measure these components, using existing and validated assessment tools wherever possible. We will draw upon measurement tools and definitions identified or endorsed by the Agency for Healthcare Research Quality (AHRQ) and National Quality Forum (NQF).²⁸⁻³² We will also rely on the expertise of our external consultants [name] (lead author of the 2014 update of the AHRQ Care Coordination Measures Atlas²⁸) and [name] (previously, Vice President for Research & Analysis, National Committee for Quality Assurance) to translate existing measures and develop supplemental measures as needed.

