4.2.2 Patients

- Age 18 or older
- Historical Cohort: Receiving care coordination services in a participating clinic with a care coordination start date between January 2018 and February 2019
- Primary Cohort: Receiving care coordination services in a participating clinic with a care coordination start date between January 2021 and December 2021

- Currently insured by the MN Department of Human Services (DHS), Blue Cross Blue Shield MN (BCBS), UCare, Medica, or HealthPartners (HP) (for utilization-based outcomes only)
- Consents to participate in interview or responds to a survey (for those data collection events only)

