4.4.3.2 Care Coordinator Survey Recruitment

Care coordinator surveys will be collected at one time point with the lead care coordinator from each participating clinic. MDH will facilitate the care coordinator survey recruitment from the smaller organizations they recruited and HPI staff will work with the study liaisons in the large groups they recruited to complete this task. Once the appropriate care coordinators have been identified, MDH or HPI staff will e-mail the electronic survey link to each lead care coordinator to complete. Non-responders will receive follow-up by HPI or MDH staff via email or phone as needed until survey completion. Recruitment will continue until all surveys are complete.

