7.3.4 Comparison between Patient Cohorts

In comparing the two cohorts with respect to Aim 1, we will test and measure whether the comparative effectiveness of the two care coordination models differs between the two cohorts (i.e., before and after COVID). For example, we might learn that the two care models were performing similarly prior to COVID, but since COVID, patients receiving attention from a social worker in the medical/social model have fared comparatively better in one or more ways. With respect to Aim 2, we will test and measure whether the core components of the comparator care models—and other factors including size of patient panels for coordination, resources available to the coordinators, duration and frequency of encounters, mode of encounter, etc.—have shifted over time or whether the individual effects of these components or factors on outcomes differ between cohorts. For example, we may learn that clinics primarily delivering care coordination in-person corresponded with better outcomes prior to COVID, but after COVID, we may learn that telemedicine is being used at greater prevalence and with similar effect as in-person care coordination services. Finally, with respect to Aim 3, we will test and measure whether organizational, community, care process, and patient factors differ between cohorts and whether any shifts in these contextual factors have had any differential effect on patient outcomes. For example, we might learn that patients are experiencing challenges with non-medical factors (i.e., “social determinants” such as housing, employment, transportation, or insurance) at greater rates now compared to before the pandemic and further that the medical/social model now has a more significant comparative effect on these patients’ outcomes, potentially as a result. Importantly, Aims 2 and 3 will help us to understand what is driving any differences in the comparative effectiveness between the two care coordination models between the two population cohorts, should they be found to exist.

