1, Yes
0, No
99, Not sure

[if at more than 1 clinic] Ask question for each specific clinic

[If yes] 12aa. Will they regularly interact with care coordination patients? [plan_add_sw_pat]

1, Yes
0, No
99, Not sure

[if at more than 1 clinic] Ask question for each specific clinic

[If yes] 12ab. Will they routinely interact with clinicians of care coordinated patients regarding their care? [plan_add_sw_clin]

1, Yes
0, No
99, Not sure

[if at more than 1 clinic] Ask question for each specific clinic

[Page break]

Now thinking about care coordination generally.

13. On average how many patients does a care coordinator work with at any given time at [clinic name]? [patients_num]

___ [require integer]

[if at more than 1 clinic] Ask question for each specific clinic

14. Does this number of patients seem like too many, about right or too few? [patients_num_load]

Too many
About right
Too few

[if at more than 1 clinic] Ask question for each specific clinic

15. On average, how many clinicians does a full-time care coordinator generally work with at any given time? [clinicians_to_cc]
____ [require integer]

16. Generally, how are patients that need care coordination identified? Please check all that apply. [identification]

- 1, Referral from clinician
- 2, Referral from other staff
- 3, High utilizers of hospital/Emergency Department care
- 4, Particular health conditions (e.g., diabetes, drug addiction, etc.)
- 5, Transition in site of care (e.g., inpatient discharged to home)
- 6, Patients identified through registry
- 7, Patients with a complex condition or multiple co-morbidities
- 8, High social needs
- 9, Patient/family request
- 99, Some other way, please specify: _____ [identification_oth]

17. Generally, about how often are each of the following forms of communication used for interactions between care coordinators and care coordination patients?

[Always used, mostly used, sometimes used, rarely used, never used]

4 3 2 1 0

- In-person meeting [communication_meet]
- Telephone [communication_phone]
- Video call [communication_video]
- Message through EMR [communication_emr]
- Some other, [communication_oth] Please specify: _____ [communication_other]

18. Who usually initiates interactions with care coordination patients? [initiate_interaction]

- 1, Most often the care coordinator initiates the interaction
- 2, About equal
- 3, Most often the patient initiates the interaction

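### For panel size, contact modality and most other clinic-level components, Aim 2 has no 2018 or pre-COVID measurement, so its Historical Cohort and change-over-time analyses cannot be validly estimated

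*Combined protocol and SAP*

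**What the plan says.** Section 7.3.2 fits models of care coordination components, treated as clinic-level variables, against each outcome, and adds: "These analyses will be replicated in each of the Primary and Historical cohorts as described in Aim 1 above". Historical patients are those with a "care coordination start date between January 2018 and February 2019" (section 4.2.2).

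Section 7.3.4 goes further. It will test whether the core components, along with matters such as "size of patient panels for coordination, resources available to the coordinators, duration and frequency of encounters, mode of encounter, etc.—have shifted over time", and also whether their individual effects on outcomes differ between the cohorts. Its worked example is in-person coordination before COVID compared with telemedicine afterwards. If the two care models compare similarly in both cohorts, the data may be combined to gain power for Aims 2 and 3.

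On the data source, section 2.2.2 says coordinators will be asked "whether any of these core components have changed in any significant way during the preceding 3 years", with a focus on 2018. Section 5.5.2 lists changes since 2017 among the survey topics. Section 4.4.3.2 states: "Care coordinator surveys will be collected at one time point with the lead care coordinator from each participating clinic".

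**The concern.** The analysis sections assume that each component has a value for the Historical period. The final coordinator questionnaire does not provide the look-back that sections 2.2.2 and 5.5.2 promise. Where no earlier value exists, following section 7.3.2 as written means using 2021-22 practice to describe care begun in 2018-19, on the far side of a pandemic that the protocol itself says disrupted care.

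Three results are then at risk: the Historical component coefficients, the tests of whether components shifted, and the tests of whether component effects differ by cohort. Aim 2 is one of three specific aims, and these results are meant to explain any difference between the cohorts.

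**Working it through.** **Step 1. Look for a 2018 or pre-COVID value in each instrument.**

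| Component | Coordinator survey (Appendix F) | Other sources | Earlier value? |
|---|---|---|---|
| Panel size | Question 13, current | Organizational survey caseload, current | None |
| Coordinator-patient modality | Question 17, current | File 1 puts office, phone, video and home visits into one count | None |
| Support resources | Question 10, current | Group-level item on budget reduction since COVID (Appendix D, section E) | Budget direction only, by group |
| Clinicians per coordinator, identification, initiation, family engagement, services, standardized assessment | Questions 15, 16, 18, 19, 27, 34-35, current | Group-level free text on other differences | None structured |
| Social-worker presence and interactions | Questions 12, 12a, 12b, before COVID | Appendix D: section D (2018), section E (pre-COVID) | Yes |
| Team personnel types | None beyond the social worker | Appendix D, sections D and E | Yes, by medical group |
| Encounter frequency and span | None | Appendix A, File 1: start date, last encounter date, count | Yes, by patient, both cohorts |

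The wording of the modality item shows the problem: "Generally, about how often are each of the following forms of communication used for interactions between care coordinators and care coordination patients". It has no pre-COVID counterpart. Patient surveys do not fill the gap, because section 2.2.2 rules them out for this purpose in the Historical Cohort on grounds of recall. The coordinator interviews cover only about 20 people.

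**Step 2. Gap between the start of coordination and measurement.** The survey date is itself inconsistent: fall 2021 in the text of section 2.2.2, Q1 2022 in Table 1, and completion by April 15, 2022 in section 10.

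- Fall 2021, taken as September to November: 28 Feb 2019 to 1 Sep 2021 is about 30 months; 1 Jan 2018 to 30 Nov 2021 is about 47 months.
- January to mid-April 2022: 28 Feb 2019 to 1 Jan 2022 is about 34 months; 1 Jan 2018 to 15 Apr 2022 is about 51 months.

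Measured from the end of 12 months' follow-up, the shortest gap is smaller: 28 Feb 2020 to 1 Jan 2022 is about 22 months, or about 18 months to 1 Sep 2021. On either survey date, the value is recorded after the Historical 12-month outcome window has closed. Section 7.3.6.4 says primary-analysis covariates are measured at or before entry to coordination.

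**Step 3. Shift test.** Let C_j be the single value for clinic j. If it is used in both cohorts, the within-clinic change is C_j − C_j = 0 for every clinic. Any difference in cohort averages reflects only which clinics and patients contribute (329 against 397 clinics, and a planned 66 against 57 patients per clinic, section 7.2).

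**Step 4. Component-by-cohort test.** Suppose the true effect b is the same in both cohorts, the Primary value is accurate, and the Historical value is misclassified so that its coefficient is λb. The interaction is then λb − b = −(1 − λ)b, which is not zero although nothing has changed.

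The size of λ cannot be derived from the documents, which give no switching rates. As illustrations for a binary component with 50% Historical prevalence and a linear effect:

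- 20% or 40% of clinics changing, equally in both directions: λ = 1 − 2(0.20) = 0.60, or 1 − 2(0.40) = 0.20.
- 20% or 40% of clinics all moving one way: λ = 50/70 = 0.71, or 50/90 = 0.56.

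The spread from 0.20 to 0.71 shows how far the answer depends on assumption.

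**Step 5. Encounter data need care.** Taking the submission periods in Appendix A as the time of the data pull, observation after the start date runs about 27.5 to 43.5 months for the Historical Cohort (28 Feb 2019 to 14 Jun 2021; 1 Jan 2018 to 15 Aug 2021). For the Primary Cohort it runs about 2.5 to 16.5 months (31 Dec 2021 to 15 Mar 2022; 1 Jan 2021 to 15 May 2022). Raw counts are therefore not comparable.

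**The case against.** The strongest reply is that earlier data do exist. Section 2.1 gives personnel, content, dose and modality as examples of components. Personnel has structured 2018 items, and dose has patient-level counts and dates in both cohorts. The organizational survey also has pre-COVID items and free text that could be coded. A reader might infer from Appendix F that neither Aim 2 question can be answered, or that everything beyond social-worker and personnel items lacks an earlier value. The documents support neither reading.

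That evidence has limits. The organizational items are at medical-group level, while the models use clinic-level components. Question 12 refers to before COVID, not 2018, and allows an answer of not sure. The last-encounter date and the count may be left blank, and File 1 does not record the length of each encounter. None of these sources supplies panel size or modality.

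It can also be said that no sentence states that 2021-22 values will be assigned to 2018-19 patients, and that section 7.1 allows planned analyses to change if data are unavailable. Both are true. But replication is promised without exception, no other source is named, and a general reservation does not say which components drop out.

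Finally, pooling is conditional and serves further analyses, so the cohort-specific Aim 2 results do not depend on it. The condition, however, concerns the two care models and would not detect a misdated component.

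**Conclusion.** The point holds for panel size, coordinator-patient modality and most other clinic-level components in Appendix F (for example questions 10, 13, 15-19, 27 and 34-35). For these there is one present-tense measurement and no structured 2018 or pre-COVID value. Historical coefficients, shift tests and component-by-cohort tests cannot be validly estimated for them, and that includes the in-person versus telemedicine example.

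It does not hold for social-worker presence and interactions, team personnel types, or encounter frequency and span, which can be studied within the limits above.

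A reader might be tempted to put the loss at 40% to 80% attenuation. That range follows only from assumed symmetric switching in 20% to 40% of clinics; one-way switching at the same rates gives about 29% to 44%. The documents support neither set of rates, so no attenuation figure should be attached. The conclusion assumes that the appendices contain the instruments as fielded. Aim 1 is outside this point.

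**What to change.** 1. In sections 7.3.2 and 7.3.4, including the pooled Aim 2 analyses, limit Historical, shift and component-by-cohort analyses to components with a recorded 2018 or pre-COVID value. These are the social-worker items (Appendix F questions 12-12b; Appendix D sections D and E), personnel types (Appendix D, stated to be at medical-group level), and File 1 encounter counts and dates expressed as rates.
2. Run all other component models in the Primary Cohort only, and replace the telemedicine example.
3. Treat any Historical analysis using 2021-22 values as supplementary and label it as assuming no change since 2018. It could be limited to medical groups reporting no 2018 differences, noting that a blank free-text answer does not prove there was no change.
4. Reconcile the coordinator survey date across sections 2.2.2 and 10 and Table 1, and align sections 2.2.2 and 5.5.2 with what Appendix F asks.

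The cost is SAP wording and fewer models. The downside is that the Historical Cohort no longer contributes to most clinic-level Aim 2 component estimates, and the power hoped for from pooling is lost for those components.
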